- Persistent fever ($>38^{\circ}\text{C}$) beyond one week after exclusion from classical causes such as malaria or pneumonia
- Persistence or aggravation of fatigue
- Chest radiographs imaging suggestive of tuberculosis

4. Case with diagnosis of tuberculosis (40,41)

- **Confirmed TB:** patients with Xpert MTB/RIF Ultra positive (or TB culture positive when available) in a respiratory sample (pulmonary TB) or in other sample, such as CSF, lymph node or other tissue/liquid (extra pulmonary TB); TB LAM positive in HIV-infected patients.
- **Unconfirmed TB:** no microbiological confirmation but clinical diagnosis of TB and started on anti TB treatment (as established in Appendix 5).
- **Unlikely TB:** good response to other treatments (antibiotic, nutritional support, etc.) and no suggestive symptoms after 1 week of admission and until the 2 month follow-up.

8. Study procedures

a. Identification of participants

Eligible children will be identified upon admission to paediatric ward, ITFC, PICU/NICU (in Bissau) or as suggestive cases in OPD. The identification of suspected TB cases will be mainly based on clinical criteria. A diagnostic algorithm (Appendix 4) will be applied to all suspected cases. The populations of interest for this study are hospitalized children, severely malnourished (SAM) and HIV positive or exposed children.

b. Laboratory

1. Sample collection

All patients included in the study will have requested one stool and one urine sample. The team will follow a specific SOP for respiratory sample collection (naso-pharyngeal aspirate, gastric lavage or spontaneous sputum), stools, urine and lymph nodes (or other validated extra pulmonary samples) as described in the appendixes. In hospitalized children, all samples will be collected during hospitalisation and patients not capable of producing the required sample (stools/urine) during this period will be excluded from the study. For ambulatory patients, samples will be collected within 2 hours and, if child not capable of producing stools/urine, samples will be requested to be brought by parents or guardians the day after.

2. Laboratory procedures

Xpert MTB/RIF Ultra will be performed to respiratory or extra pulmonary validated samples, stools and urine for all patients at baseline, and for those with negative results and persistent symptoms, will be repeated after 1 to 2 weeks.

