TB LAM in urine will be tested in all Malakal patients (starting from November 2021) and the result (negative/positive and grade 1-4) recorded in the CRF Lab form. The result will be shared with Research Manager who will only communicate to clinicians in case of HIV-infected patient; in these patients, TB LAM will be used as per clinical protocol.

3. Sample handling and storage

Respiratory specimens will be collected at the clinic and samples will be kept between 2 and 8°C until processed. Processing will be done within the 24 hours and not more than 72 hours after collection. A sterile stool container and instructions will be provided to the parent or guardian for specimen collection and handling. Following delivery to the laboratory, the stool specimen will be kept in a cool dry place and processed within 2 hours. Samples obtained in this study will adhere to all local laboratory procedures governing the storage of biological specimens.

c. Linkage to care for HIV/TB patients

All patients HIV positive will be enrolled into **HIV care** either in MSF program (Malakal) or MoH programs (Bissau). MSF will guarantee that all children will be started on ART after 2 weeks of TB treatment (or as soon as possible if TB has been excluded) or differed to 4-6 weeks in case of TB meningitis.

All TB cases (confirmed or unconfirmed) will be enrolled in **TB care** in MSF program (Malakal) or MoH program (Bissau). MSF will ensure all patients to be started on adequate weight-based dose fix combinations and followed up during the length of treatment. All children diagnosed of DRTB will be initiated on DRTB treatment regimen according to national recommendation.

In patients where stool samples yield positive results and sputum tests are negative, stool results will be communicated to Study Coordinator on site for interpretation and appropriate clinical management. Where stools results are concordant with sputum results, no additional information will be provided.

As a transversal study, it is not foreseen to follow-up patients for study purposes. The follow-up will be required though for the study “Evaluating POCUS to improve TB diagnosis in children”.

d. Data collection

The following information will be noted in an individual case study report form (CRF) for each participant:

1. DEMOGRAPHIC INFORMATION AND INFORMED CONSENT OF PATIENTS:

- Study code
- Date of birth / age
- Sex
- Parent or guardian's informed consent: Yes / No

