- Consent to be traced in case of defaulting

2. CLINICAL AND DIAGNOSTIC INFORMATION OF STUDY PARTICIPANTS AT BASELINE:

[figure not shown]
- Entry point (OPD, TB or HIV or Nutrition program, IPD)
- History of TB contact, HIV or malnutrition
- Temperature (axillary) (°C)
- Weight and size
- Nutritional status
- Co-morbidities: malaria, respiratory infection, HIV status
- Signs and clinical symptoms suggestive of tuberculosis
- Final diagnosis
- TB treatment started: Yes / No
- Date of TB treatment started

[figure not shown]
3. LAB EXAMS INFORMATION:

- Program identification number
- Inclusion number in the study
- Date of respiratory sample collection
- Type of procedure: spontaneous sputum, naso-pharyngeal aspirate, gastric aspiration
- Date of Xpert MTB/RIF Ultra in respiratory sample performed (1 sample)
- Result of Xpert MTB/RIF Ultra (negative, positive RIF resistance negative, positive RIF resistance positive, indeterminate)
- Date of stools collection
- Date of Xpert MTB/RIF Ultra in stools performed (1 or 2 samples)
- Result of Xpert MTB/RIF Ultra (negative, positive RIF resistance negative, positive RIF resistance positive, indeterminate)
- Date of urine collection
- Date of Xpert MTB/RIF Ultra in urine performed (1 or 2 samples)
- Result of Xpert MTB/RIF Ultra (negative, positive RIF resistance negative, positive RIF resistance positive, indeterminate)

e. Flow of patients

OPD patients who don't need hospitalization will be requested to stay in observation for 2 hours to perform all exams after obtaining the informed consent. If the participant is not able to produce stools within this time, s/he will be requested to bring the sample once produced at home (all information in Appendix 3). Please, find the flow in the following page.

9. Safety Considerations

There are safety considerations related to infection control of TB, even if children are only considered contagious after they acquire the capacity of expectorating (> 8 years old). For older children, isolation procedures for coughing patients, as well as protection measures for medical staff, need to be implemented. Lab staff needs to wear respirator and gloves when manipulating samples for Xpert MTB/RIF Ultra. Safety procedures related to Xpert MTB/RIF Ultra need to be in place.

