Appendix 7: SOP for gastric lavage³

Equipment required:

- Gloves and respirator
- Suction catheter (6, 7, 8F)
- Sputum container
- 50 ml syringe
- Sterile water

Performing gastric lavage:

1. Infection control measures: All personnel responsible for collecting respiratory specimens must wear personal protective equipment. The procedure will take place in a dedicated cough room or should be fitted with a door that can lock and windows that open to the outside. Alternatively, samples may be collected outside in the open air or in sputum collection booth/other appropriate structure housed outdoors.
2. Child needs to be fasting for at least 4 hours and the procedure will take place early in the morning.
3. Place the child in a half-sitting or sitting position in the adult's arms.
4. Insert a nasogastric tube and check that it is correctly placed.
5. First suction to collect the gastric fluid and place it in the sputum container, then rinse the stomach with 30 ml of sterile water and suction again. Add the suctioned fluid to the first sample.

³ Based on SOP of sputum collection in MSF TB guidelines 2014

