Appendix 10: SOP for stools Xpert MTB/RIF assay

Materials

- Xpert DX System
- Xpert Instrument, computer, barcode reader
- Xpert MTB/Rif cartridge and sample reagent bottle
- Materials required but not provided in the kit
- Centrifuge
- Gloves
- Pipette (capable of dispensing 2mL)
- Biohazard disposable bags

Safety, Health & Environment

Treat all stool specimens as potentially infectious and follow basic universal precautions. Wear protective clothing (coat/apron and gloves) when handling the specimens.

Principle

The Xpert System integrates and automates sample processing, nucleic acid amplification, and detection of the target sequences using real-time PCR and reverse transcriptase PCR. The system requires the use of single-use disposable GeneXpert MTB/Rif cartridges that hold the PCR reagents and host the PCR process. Xpert MTB/RIF includes reagents for the detection of tuberculosis and RIF resistance as well as a sample processing control (SPC) to control for adequate processing of the target bacteria and to monitor the presence of inhibitor(s) in the PCR reaction. The Probe Check Control (PCC) verifies reagent rehydration, PCR tube filling in the cartridge, probe integrity, and dye stability. The primers in the Xpert MTB/RIF assay amplify a portion of the rpoB gene containing the 81 base pair “core” region. The probes are able to differentiate between the conserved wild-type sequence and mutations in the core region that are associated with RIF resistance.

Specimen collection and storage

Collect stool samples from children in a clean wide open container. Stool samples must be processed within the day of collection. Fresh stool samples can be used within 3 hours if kept at room temperature.

Reagent storage and preparation

Xpert MTB/Rif cartridges must be stored at 2-28°C. Do not use beyond expiration date and do not open the cartridge until you are ready to perform the test (use the cartridge within 30minutes after opening its lid).

Test Procedure

- Add an aliquot of 2-3 g (pea size) of stool sample into a centrifuge tube (with a lid) using a sterile disposable plastic loop
- Add 5 ml of Phosphate Buffered Saline (PBS) and vortex to homogenize the mixture
- Centrifuge the mixture at 3200x g for 15 min

- Add 2 ml of the Xpert reagent into 1ml of the re-suspended pellet mixture and mix thoroughly.

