Appendix 11: SOP for urine Xpert MTB/RIF assay⁵

Materials

- Xpert DX System
- Xpert Instrument, computer, barcode reader
- Xpert MTB/Rif cartridge and sample reagent bottle
- Materials required but not provided in the kit
- Centrifuge
- Gloves
- Pipette (capable of dispensing 2mL)
- Biohazard disposable bags

Safety, Health & Environment

Treat all stool specimens as potentially infectious and follow basic universal precautions. Wear protective clothing (coat/apron and gloves) when handling the specimens.

Principle

The Xpert System integrates and automates sample processing, nucleic acid amplification, and detection of the target sequences using real-time PCR and reverse transcriptase PCR. The system requires the use of single-use disposable GeneXpert MTB/Rif cartridges that hold the PCR reagents and host the PCR process. Xpert MTB/RIF includes reagents for the detection of tuberculosis and RIF resistance as well as a sample processing control (SPC) to control for adequate processing of the target bacteria and to monitor the presence of inhibitor(s) in the PCR reaction. The Probe Check Control (PCC) verifies reagent rehydration, PCR tube filling in the cartridge, probe integrity, and dye stability. The primers in the Xpert MTB/RIF assay amplify a portion of the rpoB gene containing the 81 base pair “core” region. The probes are able to differentiate between the conserved wild-type sequence and mutations in the core region that are associated with RIF resistance.

Specimen collection and storage

Collect midstream urine in a fresh standard urine collection container. Fresh urine samples can be used within 3 hours if kept at room temperature.

Urine samples should be stored at 2-8°C if the test is to be run within 3 days of collection.

- If testing is delayed more than 3 days, the samples should be frozen (-20°C or colder). For frozen or refrigerated urine bring all samples to room temperature one hour prior to use. Frozen samples may contain aggregates.
- All thawed samples must be centrifuged at 3000 g for 15 minutes at room temperature. Specimens that have been frozen and thawed more than 3 times cannot be used.

Reagent storage and preparation

GeneXpert MTB/Rif cartridges must be stored at 2-28°C. Do not use beyond expiration date and do not open the cartridge until you are ready to perform the test (use the cartridge within 30minutes after opening its lid).

Test Procedure

- The sample of urine, 4ml, is centrifuged at 3000g for 5 minutes.

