Appendix 17: CRF Lab

Patient study code:

Respiratory Xpert MTB/RIF Ultra

Date of sample collection: / /

Type of procedure:

- Spontaneous sputum
- Naso-pharyngeal aspirate
- Gastric aspiration

Date of Xpert MTB/RIF performed: / /

Result of Xpert MTB/RIF:

- Negative
- Positive RIF resistance negative
- Positive RIF resistance positive
- Indeterminate

Respiratory Xpert MTB/RIF Ultra (second sample if done)

Date of respiratory sample collection: / /

Type of procedure:

- Spontaneous sputum
- Naso-pharyngeal aspirate
- Gastric aspiration

Date of Xpert MTB/RIF in respiratory sample performed: / /

Result of Xpert MTB/RIF:

- Negative
- Positive RIF resistance negative
- Positive RIF resistance positive
- Indeterminate

Validated extra pulmonary Xpert MTB/RIF Ultra

Date of sample collection: / /

Type of sample:

- Lymph node
- Pus or tissue Specify location:
- Pleural effusion
- CSF
- Ascetic fluid
- Other Specify:

Date of Xpert MTB/RIF in respiratory sample performed: / /

Result of Xpert MTB/RIF:

- Negative
- Positive RIF resistance negative
- Positive RIF resistance positive
- Indeterminate

Validated extra pulmonary Xpert MTB/RIF Ultra

Date of sample collection: / /

Type of sample:

- Lymph node
- Pus or tissue Specify location:

Pleural effusion

CSF

Ascetic fluid

Other

Specify:

Date of Xpert MTB/RIF in respiratory sample performed: / /

Result of Xpert MTB/RIF:

Negative

Positive RIF resistance negative

Positive RIF resistance positive

Indeterminate

Stools Xpert MTB/RIF Ultra

Date of stools collection: / /

Date of Xpert MTB/RIF in stools performed: / /

Result of Xpert MTB/RIF:

Negative

Positive RIF resistance negative

Positive RIF resistance positive

Indeterminate

Stools Xpert MTB/RIF Ultra (second sample if done)

Date of stools collection: / /

Date of Xpert MTB/RIF in stools performed: / /

Result of Xpert MTB/RIF:

Negative

Positive RIF resistance negative

Positive RIF resistance positive

Indeterminate

Urine Xpert MTB/RIF Ultra

Date of urine collection: / /

Date of Xpert MTB/RIF in urine performed:

Result of Xpert MTB/RIF:

Negative

Positive RIF resistance negative

Positive RIF resistance positive

Indeterminate

Urine Xpert MTB/RIF Ultra (second sample if done)

Date of urine collection: / /

Date of Xpert MTB/RIF in urine performed: / /

Result of Xpert MTB/RIF:

Negative

Positive RIF resistance negative

Positive RIF resistance positive

Indeterminate

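### Outpatient sampling rules do not ensure that the SOP limits for home-produced stool, unrefrigerated urine and gastric lavage are met, and the lab CRF can detect only some breaches

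*Combined protocol and SAP*

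**What the plan says.** **Outpatient schedule.** Under section 8.e, outpatients who do not need admission are "requested to stay in observation for 2 hours to perform all exams". Section 8.b.1 gives the same 2 hours for sample collection. If the child produces no stool or urine in that time, "samples will be requested to be brought by parents or guardians the day after". Section 8.e repeats the home option without naming a day and refers to Appendix 3 for the caretaker's instructions.

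**Stool handling.** Section 8.b.3 says that, once delivered to the laboratory, "the stool specimen will be kept in a cool dry place and processed within 2 hours". Appendix 10 is stricter and uses a different starting point: "Stool samples must be processed within the day of collection. Fresh stool samples can be used within 3 hours if kept at room temperature". It gives no refrigerated alternative.

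**Urine handling.** Appendix 11 says: "Fresh urine samples can be used within 3 hours if kept at room temperature". It also allows up to 3 days at 2-8°C, and freezing beyond that.

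**Gastric lavage.** Appendix 5 assigns lavage to children from 5 years until they can expectorate. Appendix 7 sets the condition: "Child needs to be fasting for at least 4 hours and the procedure will take place early in the morning".

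**What is recorded.** Appendix 17 has fields such as "Date of stools collection" and the date of the Xpert run for each specimen. It has no clock times, place of collection, storage or fasting item. Procedure type is recorded there, and entry point (including OPD) in Appendix 4.

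**The concern.** The main outcome (section 10) is the sensitivity and specificity of stool and urine Xpert Ultra against Xpert Ultra on a respiratory or validated extrapulmonary sample. Handling can disturb either side of that comparison.

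- **Index side.** If an over-age stool or urine loses detectable DNA, a missed case is charged to the test when the cause is handling.
- **Reference side.** If an unfasted lavage has lower yield, or the lavage is not done, a child with TB may be classed as reference-negative or have no reference result. A correct stool positive in a child classed as reference-negative then counts as a false positive.

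Both risks fall on outpatients. Without the times, the analysis cannot fully separate a handling effect from test performance.

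**Working it through.** **1. Home stool against the two sets of rules.** Take a stool passed at 18:00 and delivered at 09:00 the next day.
- Age on arrival: 6 h to midnight + 9 h = 15 h.
- Age at processing if the laboratory uses its full 2 h: 15 + 2 = 17 h.
- Section 8.b.1 is met (brought the next day), and so is section 8.b.3 (within 2 h of delivery).
- Appendix 10 is breached on the same-day rule, and on the 3-hour rule if the sample stayed at room temperature.

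For a stool passed at home on the morning of return and kept at room temperature, the time left from passing to delivery, if the laboratory uses its full allowance, is 3 − 2 = 1 h. No section in the supplied text limits that interval.

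**2. Urine.** The same timeline breaches Appendix 11 only if the sample was unrefrigerated. At 2-8°C, 17 h is well inside 3 days.

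**3. Gastric lavage.** The stay gives 2 h and the fast is at least 4 h. A child must therefore arrive already fasted for at least 4 − 2 = 2 h, early in the morning. A child fed just before arrival cannot comply within the stay, and the next-day fallback in section 8.b.1 names only stool and urine.

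**4. What the CRF can show.**

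| Breach | Visible in Appendix 17? |
|---|---|
| Stool kept overnight | Yes, collection and test dates differ, provided the collection date is the date of passing and not of receipt (the form does not say) |
| Same-day stool or urine older than 3 h | No |
| Unfasted outpatient lavage | No; outpatient lavages can be listed from entry point and procedure type, but fasting is not recorded |

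**5. The plan's own sample size (section 7.d.4).** With expected sensitivity p = 0.60 and precision d = 0.12, n = 1.96² × 0.60 × 0.40 / 0.12² = 64.0, as stated. Then 64 / 0.20 = 320 suspected cases, and 320 / 0.98 = 326.5, so 327. These figures reproduce and are not in dispute.

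**6. Range of effect, all inputs assumed.** The documents give no outpatient share, no late-sample share and no loss of detection with age.
- *Samples kept, detection reduced.* Expected sensitivity = 0.60 × (1 − share affected × relative loss). With 10% affected and a 10% loss: 0.60 × 0.99 = 59.4%. With 30% affected and a 50% loss: 0.60 × 0.85 = 51.0%. An intermediate case: if 10 to 19 of the 64 confirmed cases have an over-age stool and detection in them falls from 60% to 40%, sensitivity is (0.6 × 54 + 0.4 × 10) / 64 = 56.9% to (0.6 × 45 + 0.4 × 19) / 64 = 54.1%.
- *Samples excluded.* Half-width = 1.96 × √(0.24 / m), where m is the number of confirmed cases left.

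| Confirmed cases without an in-window sample | m | Half-width (points) |
|---|---|---|
| 0% | 64 | 12.0 |
| 5% | 60.8 | 12.3 |
| 10% | 57.6 | 12.7 |
| 20% | 51.2 | 13.4 |
| 30% | 44.8 | 14.3 |

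- *Specificity.* The plan implies 320 − 64 = 256 reference-negative children. Each stool-positive child with TB misclassed as reference-negative lowers stool specificity by about 1/256 = 0.4 point.

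**The case against.** A reader might infer that outpatient samples cannot meet the SOP limits, that outpatient index and reference samples are therefore degraded or missing, and that they cannot be identified. The documents do not support that reading.

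- A sample passed on site can comply. So can a stool passed at home on the morning of return and delivered promptly, and so can a lavage in a child who arrives fasted.
- The 3-hour stool limit is conditional on room temperature, and section 8.b.3 asks for cool storage after delivery. Urine may be refrigerated for 3 days.
- The fasting condition touches only gastric lavage. Nasopharyngeal aspirate and sputum carry no such condition; Appendix 8 already foresees a next-morning sputum, possibly collected at home; and section 8.b.3 lets respiratory samples be held for up to 72 hours. Section 8.b.2 repeats testing after 1 to 2 weeks in negative children with persistent symptoms, so one poor lavage is not always the final reference.
- The CRF dates and the OPD entry point allow overnight samples and outpatient lavages to be picked out.
- Appendix 3 is not in the supplied text, so home-storage rules cannot be called absent.
- No effect size is documented. Losses of a few points, such as the intermediate case above, lie inside the planned ±12 points. Section 8.a also names hospitalised children among the populations of interest, so the outpatient share may be small.

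All of this stands and limits the point. It does not remove it. The same-day stool rule is not conditional on temperature, and the body allows it to be broken. The lavage fallback is not stated. Whatever Appendix 3 says, the CRF cannot verify a 3-hour interval or a fast. Nor does the ±12 points excuse a handling loss: that figure is sampling error, whereas handling loss would shift the estimate in one direction.

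**Conclusion.** The concern holds in limited form. For home-produced outpatient stool, rules stated in the body permit specimens that the plan's own SOP rules out. For urine the conflict arises only without refrigeration. On the reference side it is confined to outpatient gastric lavage in children who do not arrive fasted. Detection is partial: overnight samples can be flagged if the collection date is the date of passing, but same-day samples older than 3 hours and unfasted lavages cannot.

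The size is unknown. Under the assumed ranges, expected sensitivity would move from 60% to somewhere between 59.4% and 51.0%; these are illustrations, not estimates. A reader might take a loss of 3 to 6 points (60% to 56.9% or 54.1%) as a finding. The arithmetic is correct, but both the affected share and the drop in detection are assumed. The point merits correction because the fix is cheap and protects the primary accuracy estimates, not because harm has been shown.

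**What to change.** 1. Reconcile sections 8.b.1, 8.b.3 and 8.e with Appendices 7, 10 and 11, and with Appendix 3, so that one production-to-processing limit applies to home stool and to home urine. Count it from the moment the sample is passed and state the storage condition it assumes.
2. Make the outpatient schedule and the lavage fasting condition agree. Which of them changes is for the investigators to decide.
3. Add to Appendix 17 the clock time of collection and of processing, the place of collection (home or clinic), and hours fasted for gastric lavage. Define the collection date as the date the sample was passed.
4. Test out-of-window samples and flag them, rather than dropping them silently.
5. Report stool and urine sensitivity and specificity in all samples and, additionally, in within-window samples only.

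Cost: SOP wording, a few CRF fields, and some repeat samples or return visits. The added analysis will have fewer confirmed cases and wider intervals, as tabulated above.
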